12.2.2 Responsibility for Data Submission

For ETCTN trials, it is the responsibility of the PI(s) at the site to ensure that all investigators at the ETCTN Sites understand the procedures for data submission for each ETCTN protocol and that protocol specified data are submitted accurately and in a timely manner to the CTMS via the electronic data capture system, Medidata Rave.

Data are to be submitted via Medidata Rave to CTMS on a real-time basis, but no less than once

every 2 weeks. The timeliness of data submissions and timeliness in resolving data queries will be tracked by CTMS. Metrics for timeliness will be followed and assessed on a quarterly basis. For the purpose of Institutional Performance Monitoring, data will be considered delinquent if it is greater than 4 weeks past due.

Data from Medidata Rave and CTEP-AERS is reviewed by the CTMS on an ongoing basis as data is received. Queries will be issued by CTMS directly within Rave. The queries will appear on the Task Summary Tab within Rave for the CRA at the ETCTN to resolve. Monthly web-based reports are posted for review by the Drug Monitors in the IDB, CTEP. Onsite audits will be conducted by the CTMS to ensure compliance with regulatory requirements, GCP, and NCI policies and procedures with the overarching goal of ensuring the integrity of data generated from NCI-sponsored clinical trials, as described in the ETCTN Program Guidelines, which may be found on the CTEP (http://ctep.cancer.gov/protocolDevelopment/electronic_applications/adverse_events.htm) and CTSU websites.

CTMS will utilize a core set of eCRFs that are Cancer Data Standards Registry and Repository (caDSR) compliant (<http://cbiit.nci.nih.gov/ncip/biomedical-informatics-resources/interoperability-and-semantics/metadata-and-models>). Customized eCRFs will be included when appropriate to meet unique study requirements. The PI is encouraged to review the eCRFs, working closely with CTMS to ensure prospectively that all required items are appropriately captured in the eCRFs prior to study activation. CTMS will prepare the eCRFs with built-in edit checks to the extent possible to promote data integrity.

CDUS data submissions for ETCTN trials activated after March 1, 2014, will be carried out by the CTMS contractor, Theradex. CDUS submissions are performed by Theradex on a monthly basis. The trial's lead institution is responsible for timely submission to CTMS via Rave, as above.

Further information on data submission procedures can be found in the ETCTN Program Guidelines (http://ctep.cancer.gov/protocolDevelopment/electronic_applications/adverse_events.htm).

Study participants are responsible for submitting CDUS data and/or data forms to either the Coordinating Center or to the Lead Organization on the study quarterly. The date for submission to the Coordinating Center or to the Lead Organization will be set by them. CDUS does not accept data submissions from the participants on the study. When setting the dates, allow time for Coordinating Center compilation, Principal Investigator review, and timely submission to CTEP by the quarterly deadlines (see Section [12.2.1](#)). For trials monitored by CTMS, a quarterly report of data will be provided by Theradex to the Coordinating Center.

Either the Coordinating Center or the Lead Organization is responsible for compiling and submitting CDUS data to CTEP for all participants and for providing the data to the Principal Investigator for review.

12.3 Data Quality Portal

The Data Quality Portal (DQP) provides a central location for site staff to manage unanswered queries and form delinquencies, monitor data quality and timeliness, generate reports, and review metrics.

The DQP is located on the CTSU members' website under Data Management. The Rave Home section displays a table providing summary counts of Total Delinquencies and Total Queries. DQP Queries, DQP Delinquent Forms, and the DQP Reports modules are available to access details and reports of unanswered queries, delinquent forms, and timeliness reports. Review the DQP modules on a regular basis to manage specified queries and delinquent forms.

The DQP is accessible by site staff that are rostered to a site and have access to the CTSU website. Staff that have Rave study access can access the Rave study data using a direct link on the DQP.

To learn more about DQP use and access, click on the Help icon displayed on the Rave Home, DQP Queries, and DQP Delinquent Forms modules.

Note: Some Rave protocols may not have delinquent form details or reports specified on the DQP. A protocol must have the Calendar functionality implemented in Rave by the Lead Protocol Organization (LPO) for delinquent form details and reports to be available on the DQP. Site staff should contact the LPO Data Manager for their protocol regarding questions about Rave Calendaring functionality.

12.4 Human Data Sharing Plan

What data will be shared?

We will share human data generated in this research for future research as follows:

- x De-identified data in an NIH-funded or approved public repository
- x Identified data in BTRIS (automatic for activities in the NIH Clinical Center)
- x De-identified or identified data with approved outside collaborators under appropriate agreements

How and where will the data be shared?

Data will be shared through:

- x An NIH-funded or approved public repository: clinicaltrials.gov
- x BTRIS (automatic for activities in the NIH Clinical Center)
- x Approved outside collaborators under appropriate individual agreements
- x Publication and/or public presentations

When will the data be shared?

- x At the time of publication or shortly thereafter

12.5 Collaborative Agreements Language

The agent(s) supplied by CTEP, DCTD, NCI used in this protocol is/are provided to the NCI under a Collaborative Agreement (CRADA, CTA, CSA) between the Pharmaceutical Company(ies) (hereinafter referred to as “Collaborator(s)”) and the NCI Division of Cancer Treatment and Diagnosis. Therefore, the following obligations/guidelines, in addition to the provisions in the “Intellectual Property Option to Collaborator” (http://ctep.cancer.gov/industryCollaborations2/intellectual_property.htm) contained within the terms of award, apply to the use of the Agent(s) in this study:

1. Agent(s) may not be used for any purpose outside the scope of this protocol, nor can Agent(s) be transferred or licensed to any party not participating in the clinical study. Collaborator(s) data for Agent(s) are confidential and proprietary to Collaborator(s) and shall be maintained as such by the investigators. The protocol documents for studies utilizing Agents contain confidential information and should not be shared or distributed without the permission of the NCI. If a copy of this protocol is requested by a patient or patient’s family member participating on the study, the individual should sign a confidentiality agreement. A suitable model agreement can be downloaded from: <http://ctep.cancer.gov>.
2. For a clinical protocol where there is an investigational Agent used in combination with (an)other Agent(s), each the subject of different Collaborative Agreements, the access to and use of data by each Collaborator shall be as follows (data pertaining to such combination use shall hereinafter be referred to as "Multi-Party Data"):
 - a. NCI will provide all Collaborators with prior written notice regarding the existence and nature of any agreements governing their collaboration with NCI, the design of the proposed combination protocol, and the existence of any obligations that would tend to restrict NCI's participation in the proposed combination protocol.
 - b. Each Collaborator shall agree to permit use of the Multi-Party Data from the clinical trial by any other Collaborator solely to the extent necessary to allow said other Collaborator to develop, obtain regulatory approval or commercialize its own Agent.
 - c. Any Collaborator having the right to use the Multi-Party Data from these trials must agree in writing prior to the commencement of the trials that it will use the Multi-Party Data solely for development, regulatory approval, and commercialization of its own Agent.
3. Clinical Trial Data and Results and Raw Data developed under a Collaborative Agreement will be made available to Collaborator(s), the NCI, and the FDA, as appropriate and unless additional disclosure is required by law or court order as described in the IP Option to Collaborator (http://ctep.cancer.gov/industryCollaborations2/intellectual_property.htm). Additionally, all Clinical Data and Results and Raw Data will be collected, used and disclosed consistent with all applicable federal statutes and regulations for the protection of human subjects, including, if applicable, the *Standards for Privacy of Individually Identifiable Health Information* set forth in 45 C.F.R. Part 164.

4. When a Collaborator wishes to initiate a data request, the request should first be sent to the NCI, who will then notify the appropriate investigators (Group Chair for Cooperative Group studies, or PI for other studies) of Collaborator's wish to contact them.
5. Any data provided to Collaborator(s) for Phase 3 studies must be in accordance with the guidelines and policies of the responsible Data Monitoring Committee (DMC), if there is a DMC for this clinical trial.
6. Any manuscripts reporting the results of this clinical trial must be provided to CTEP by the Group office for Cooperative Group studies or by the principal investigator for non-Cooperative Group studies for immediate delivery to Collaborator(s) for advisory review and comment prior to submission for publication. Collaborator(s) will have 30 days from the date of receipt for review. Collaborator shall have the right to request that publication be delayed for up to an additional 30 days in order to ensure that Collaborator's confidential and proprietary data, in addition to Collaborator(s)'s intellectual property rights, are protected. Copies of abstracts must be provided to CTEP for forwarding to Collaborator(s) for courtesy review as soon as possible and preferably at least three (3) days prior to submission, but in any case, prior to presentation at the meeting or publication in the proceedings. Press releases and other media presentations must also be forwarded to CTEP prior to release. Copies of any manuscript, abstract and/or press release/ media presentation should be sent to:

Email: [contact]

The Regulatory Affairs Branch will then distribute them to Collaborator(s). No publication, manuscript or other form of public disclosure shall contain any of Collaborator's confidential/proprietary information.

12.6 Genomic Data Sharing Plan

The NIH Genomic Data Sharing (GDS) Policy ensures broad and responsible sharing of genomic research data from all NIH-funded research (<https://gds.nih.gov/index.html>). Providing that patient consent has been obtained, targeted sequencing, whole-exome sequencing, and RNA-seq data generated for research purposes will be submitted to the Database of Genotypes and Phenotypes (dbGaP) for controlled-access use within a time frame consistent with data publication. The identities of research participants will not be disclosed to dbGaP or to secondary users of the data.

13. STATISTICAL CONSIDERATIONS

13.1 Study Design/Endpoints

This study will enroll adult and pediatric patients, but only adults will be included in the primary and interim analyses. For adult patients, a Simon two stage design will be employed within each of the three study cohorts, with a maximum of 17 evaluable patients per cohort. For each cohort, accrual will be halted at 9 patients to evaluate for response before further enrollment. If within 9

months of the ninth patient being enrolled to a cohort no responses are observed among the initial 9 patients in that cohort, the cohort will be terminated early and declared negative; if at least one response is observed, accrual to that cohort will continue. If at least 3 responses (at least 17.6%) are observed among the initial 17 evaluable patients in a disease cohort, this regimen will be considered worthy of further testing in that disease. This design yields at least 81% power to detect a true response rate of at least 25% in each cohort. It yields at least .95 probability of a negative result if the true response rate in each cohort is no more than 5%, with at least .63 probability of early negative stopping for each cohort. Per the RECIST v 1.1 guidelines ([Section 13.4.2](#)), all eligible patients who are treated on study will be included in the primary and interim response analyses.

The trial will remain open to pediatric patients with CCS and CS for as long the study is accruing, up to a maximum of 8 pediatric patients across the three study histologies. These patients will not provide research biopsies, but will have the opportunity to be treated due to the possibility of therapeutic benefit. Within each cohort, a maximum of 2 pediatric patients will be enrolled prior to the completion of the first-stage futility analysis. If none of the initial 9 adult patients enrolled to a cohort respond within 9 months of the ninth adult patient being enrolled, no additional adult or pediatric patients with that histology will be enrolled. If accrual of adult patients proceeds to the second stage within a cohort, additional pediatric patients with that histology may be enrolled until the 17th adult patient is enrolled (as long as the limit of 8 total pediatric patients across all cohorts has not been reached), at which point all accrual of patients with this histology will be halted.

If the study is found to be positive (i.e. at least 3 objective responses are observed) within a cohort and the accrual limit for that cohort has been reached prior to obtaining 10 evaluable biopsy pairs, an amendment will be submitted to CTEP to increase the accrual limit for this cohort so that ten evaluable biopsy pairs can be obtained (if feasible).

13.2 Sample Size/Accrual Rate

Each of the three cohorts, made up of adult and pediatric patients, will have up to 17 evaluable patients. To allow for a small number of patients who may not be evaluable, the accrual ceiling will be set at 68. We anticipate that 1-2 patients per month will be enrolled to study. The table below includes accrual estimates for the duration of the study.

PLANNED ENROLLMENT REPORT

Racial Categories	Ethnic Categories				Total
	Not Hispanic or Latino		Hispanic or Latino		
	Female	Male	Female	Male	
American Indian/ Alaska Native					
Asian	3	4			7

Racial Categories	Ethnic Categories				Total
	Not Hispanic or Latino		Hispanic or Latino		
	Female	Male	Female	Male	
Native Hawaiian or Other Pacific Islander	1	1			2
Black or African American	8	8		1	17
White	14	17	4	5	40
More Than One Race	1	1			2
Total	27	317	4	6	68

13.3 Analysis of Secondary Endpoints

Mandatory biopsies will be collected for pharmacodynamic analysis from adult patients only. As there are differences in biological characteristics among sarcoma subtypes, pharmacodynamic comparisons will only be made within the CS and CCS sarcoma cohorts, rather than CCS and CS samples being pooled for analysis. Biopsy pairs will be collected from 15 adult patients from each disease cohort. With 15 biopsy pairs collected from each cohort, there will be 95% likelihood of getting at least 10 evaluable biopsy pairs from each cohort. For a given PD endpoint within each cohort, 10 evaluable biopsy pairs will yield 86% power to detect a difference in change from baseline to post-treatment, between the clinical responders and the non-responders, corresponding to at least 2.5 SD's (with respect to the changes from baseline within each subgroup), at the 1-sided .01 significance level (to accommodate multiple comparisons).

If the study is found to be positive (i.e., at least 3 objective responses are observed) within a cohort and the accrual limit for that cohort has been reached prior to obtaining 15 biopsy pairs (or 10 evaluable biopsy pairs), an amendment will be submitted to CTEP to increase the accrual limit for this cohort so that 10 evaluable biopsy pairs can be obtained (if feasible).

Exploratory evaluations will also be performed, with results reported with appropriate caveats about the exploratory nature of the analysis, and without formal adjustment for multiple comparisons.

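### Section 13.3's 86% power for the responder versus non-responder biopsy comparison cannot be reached with 10 pairs by a two-sample t-test at any split; the figure is 62% to 81% with 2 to 4 responders

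*Combined protocol and SAP*

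**What the plan says.** Section 13.3 plans 15 biopsy pairs per cohort, with a 95% chance that at least 10 are evaluable, and bases its power statement on 10: "10 evaluable biopsy pairs will yield 86% power to detect a difference in change from baseline to post-treatment". The comparison is "between the clinical responders and the non-responders", the effect is a difference "corresponding to at least 2.5 SD" of the within-group changes, and the test is made "at the 1-sided .01 significance level (to accommodate multiple comparisons". No test statistic, formula or division of the 10 pairs into responders and non-responders is given.

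Section 13.1 supplies the only response rates in the statistical section. The design has 81% power to "detect a true response rate of at least 25% in each cohort", the uninteresting rate is 5%, and the success rule reads "If at least 3 responses (at least 17.6%) are observed among the initial 17 evaluable patients".

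The comparison serves secondary objective 1.2.3 (activated CD8+ T cells in the tumor and their relation to response). Sections 13.1 and 13.3 also make 10 evaluable pairs an operational target: a positive cohort that fills before reaching that number leads to an amendment raising its accrual limit.

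**The concern.** Ten observations in two unequal groups leave 8 degrees of freedom for the SD, and at one-sided .01 that costs a good deal of power compared with treating the SD as known. The groups will probably be very unequal, because the target response rate is 25% and a cohort can succeed with 3 responders in 17. A figure as high as 86% therefore needed checking.

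At stake is what a non-significant comparison can tell us. At 86% power, a true 2.5 SD difference would be missed 14% of the time. At 62% to 75% it would be missed 38% to 25% of the time. The same figure is the only quantitative reason given for treating 10 evaluable pairs as enough.

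**Working it through.** **Inputs from section 13.3:** N = 10 evaluable pairs, difference d = 2.5 within-group SDs, one-sided alpha = 0.01.

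**Assumption:** the number of responders n1 among the 10, with n2 = 10 − n1. The documents do not give it, so 1 to 5 are shown. The 25% target rate in section 13.1 implies 2.5, and the integer splits on either side are 2:8 and 3:7.

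**Formulas.** Noncentrality: δ = 2.5 × √(n1 × n2 / 10).

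- Normal approximation (SD known): power = Φ(δ − 2.326).
- Two-sample pooled t-test (SD estimated): power = P(T > 2.896), where T is noncentral t with 8 df and noncentrality δ.

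**Reproducing the stated figure.** At 2.5:7.5, δ = 2.5 × √(18.75/10) = 3.423, and Φ(3.423 − 2.326) = 0.864. This matches 86%. The t-test at the same fractional split gives 0.694.

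**Recalculating by split.**

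| Responders : non-responders | δ | Normal approximation | t-test, 8 df | Difference needed for 86% by t-test |
|---|---|---|---|---|
| 1:9 | 2.372 | 51.8% | 36.4% | 4.36 SD |
| 2:8 | 3.162 | 79.8% | 61.7% | 3.27 SD |
| 3:7 | 3.623 | 90.3% | 74.8% | 2.85 SD |
| 4:6 | 3.873 | 93.9% | 80.8% | 2.67 SD |
| 5:5 | 3.953 | 94.8% | 82.5% | 2.62 SD |

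The t-test maximum, at an even split, is 82.5%, so 86% is out of reach for every division of 10 pairs.

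**Averaging over the split.** If the number of responders is Binomial(10, 0.25), the probabilities of 0 to 6 responders are 0.056, 0.188, 0.282, 0.250, 0.146, 0.058 and 0.016. Weighting the t-test powers by these, with no power at 0 responders and the mirrored value at 6 and above, gives 0.611. The probability of 0 or 1 responders is 0.056 + 0.188 = 0.244. At a response rate of 3/17, the success threshold, the average is 0.489.

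**Other tests.** At 2:8 and 3:7, simulated power for the unequal-variance (Welch) t-test is about 39% and 54%. For the exact Wilcoxon test it is 0% and about 63%; at 2:8 its smallest possible one-sided p-value is 1/45 = 0.022. The pooled t-test with normal data is therefore the favourable case at these splits.

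**The case against.** **The derivation is not known.** Other routes come within two points of 86%: a two-sided .01 normal approximation at 3:7 (85.2%), a rough form Φ(δ − 2.896) at 5:5 (85.5%), and an exact t-test on 15 pairs split 3:12 (87.1%). Each fits the text less well: the text says one-sided, the design targets 25% response, and the statement is about 10 pairs. This objection stands to the extent that the normal approximation is the best-fitting explanation and not an established fact. The finding that a t-test on 10 pairs cannot give 86% does not depend on it.

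**Ten pairs is a floor.** A 95% chance of at least 10 from 15 implies that about 81% of pairs are evaluable, so about 15 × 0.81 ≈ 12 are expected. With 12 pairs the t-test has 82% power at 3:9 and 88% at 4:8, and 13 pairs at an exact 25% split would give 86%. This stands: the trial may well do better than the 10-pair figures. It does not rescue the printed sentence, which concerns 10 pairs. Averaged over Binomial(12, 0.25), power is still only about 73%.

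**The shortfall depends on the split.** This also stands. It is about 24 points at 2:8 and 11 at 3:7, but only about 5 at 4:6 and 3.5 at 5:5.

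**Stronger readings.** A reader might infer that a null result will be presented as adequately powered. Nothing in the documents says so; it is a risk created by the sentence. Nor do the paired biopsies lose their purpose: section 9 also uses them for PD-1/PD-L1 expression and sequencing. A reader might also infer from the rank-test limit that the comparison is impossible with 2 responders, but the plan specifies no rank test, and the limit does not apply at 3:7 (1/120 = 0.0083).

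**Conclusion.** The 86% in section 13.3 is wrong as written for any two-sample t-test on 10 evaluable pairs that estimates the SD. With 2, 3 or 4 responders, power for 2.5 SD at one-sided .01 is about 62%, 75% or 81%; the ceiling is 82%, and the average at a 25% response rate is about 61%. These figures assume normally distributed changes with equal variance in the two groups and exactly 10 pairs. The split is an assumption taken from the 25% design rate; the direction of the error is the same at every split.

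The point should be fixed, but it is confined to a secondary pharmacodynamic endpoint. The go/no-go rule in section 13.1 rests on objective response and is untouched.

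It might be tempting to conclude that the responder comparison should give way to a correlation with tumor shrinkage as the main analysis. The documents give no expected correlation on which to judge such a change. Percent change in target lesions also misses progression through new or non-target lesions, and it is unavailable for patients with no follow-up scan, whom section 13.4.2 keeps in the response analysis as failures. Correcting the power statement does not require that redesign.

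**What to change.** In section 13.3, name the test, state the assumed number of responders among the evaluable pairs, and replace the 86% statement. Suggested wording, if the pooled t-test is intended:

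> With 10 evaluable pairs, a two-sample t-test at one-sided .01 has about 62%, 75% or 81% power for a 2.5 SD difference with 2, 3 or 4 responders. Power of 86% requires a difference of about 3.3, 2.9 or 2.7 SD respectively.

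If a Welch or rank test is intended, the figures must be recomputed for that test; at 2:8 and 3:7 they will be lower.

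The cost is a wording amendment with no new data, procedures or patients. The downside is that the stated power becomes less favourable. The authors may then wish to say whether 10 evaluable pairs remains the target that triggers an accrual amendment.
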